4.0 Resources and Personnel

Drs. [name] and [name] will train the research team to administer verbal consent and administer and score the assessment measures through instruction and observed role play. Interventionists with at least a master's degree and prior CBT training will deliver BEAST. Drs. [name] and [name] will train the interventionists using the PowerPoint slide deck. We will monitor treatment fidelity (i.e., adherence and competence) by audio-recording intervention sessions

(via Teams or Webex) and reviewing them in weekly supervision meetings. Weekly meetings will be provided by Drs. [name] and [name]. The meetings will focus on all of the issues involved in study tasks including: a) recruiting participants, b) conducting interviews, c) coding interview data, d) communicating between research staff and interventionists, e) contacting participants for follow-up assessment; f) completing documentation, and g) storing and safeguarding data. To maintain blinding, separate meetings among interventionists and the coordinator will be done as needed. The interventionist will complete intervention sheets electronically to track beliefs identified. These will be monitored, in addition to the recorded sessions, during ongoing supervision.

PI [name] will train the project staff in coordination with Co-Is [name] and [name]. [name] will train the Project Coordinator to track recruitment and retention as well as data fidelity. [name] will supervise and train the Project Coordinator to address IRB and grant-related documentation and to monitor the data stream from the mobile app and contact participants as-needed when compliance issues for completion of surveys via mobile app arise.

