Assessments and Intervention: Veterans will be enrolled following informed consent. Veterans will next complete the baseline assessment. At the baseline assessment, Veterans meet with the Project Coordinator by phone or virtually to complete a consenting process, guidance on the video software being used, and set-up and guidance of the mobile app. Research team member will reach out to the Veteran the following day to address any issues with using the app. Veteran will complete assessment surveys for approximately 1 week. At the baseline appointment, participants will be scheduled to receive the face-to-face virtual intervention followed by two weeks of EMA/EMI via mPRO. At the end of the two weeks, Veterans will complete a post-intervention assessment appointment. Follow-up assessment appointments will be completed at the 1-month and 3-month follow-ups. The post-intervention assessment includes an exit interview for participants to provide additional feedback regarding acceptability of the intervention. The research staff will read the measures to the Veteran who will verbally provide their answers; we have found this improves data reliability and completeness immensely compared to mailing packets/sending survey links.

BEAST contains two components: First, there is a single session **face-to-face virtual intervention** delivered by the counselor or therapist, delivered via VA Video Connect software. Second, a **mobile app (mPRO) is used for EMA and to deliver EMI components.**

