Face-to-face session. The face-to-face session is a one-hour manualized intervention that uses interactive content to enhance participant learning of critical intervention components. The session includes 1) psychoeducation regarding the role of anxiety sensitivity in exacerbating anxiety sensations, 2) practice identifying and challenging maladaptive thoughts about anxiety, and 3) an IE activity. Psychoeducation is first provided, focusing on the body's alarm system with a goal of normalizing bodily sensations associated with anxiety. Following psychoeducation, the participant and therapist discuss sensations the participant experiences when they are anxious and the thoughts about these sensations that serve to maintain them. The participant and therapist explore challenges to any strongly held beliefs about the danger of anxiety sensations. Finally, the IE consists of: repeated trials of hyperventilation given evidence that this challenge is among the most anxiety-provoking for individuals with panic disorder and our experience using this IE exercise in prior RCTs,¹⁰⁻¹² as well as repeated trials of another selected interoceptive exposure activity. To aid in personalization, Veterans assist in choosing 3 **key takeaways** that summarize what they learned from the intervention regarding anxiety sensations as benign. Common summaries from past participants include: *Anxiety sucks, but it is harmless; I've been anxious before, no big deal!* These summary phrases are incorporated into the EMI. Participants are also asked to complete one set of IE exercises daily for the next two weeks.

EMA. EMA will be collected from baseline to post-intervention and for one week after completing each follow-up. This measurement burst design allows for ratings of functional impairment and anxiety to be calculated disambiguated from state level influences. In our future RCT, this will provide additional power to explore the mechanisms at play. Consistent with best-practice recommendations¹³ we will employ a mixture of *fixed time-based sampling*, *experience sampling*, and *event-based sampling* strategies. In the morning, participants will receive a fixed time-based survey that will include a short battery of questions that will take approximately 2

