minutes to complete. Experience sampling will be used to deliver three surveys, distributed quasi-randomly over the remainder of the day (each take 30s to 1 minute to complete). Pulses are randomized such that they are never less than 3 hours and never more than 8 hours apart. Finally, event-based sampling will be used for tracking IE exercise completion.

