5.5 Study Evaluations

Consistent with recommendations for determining acceptability and feasibility in the context of intervention development, multiple program aspects will be evaluated with the aim of refining BEAST for larger-scale implementation.^{15–17} Feasibility of BEAST will be indexed via participant retention, average homework completion, and percentage of EMA sessions completed.

Acceptability will be measured using an adaptation of the Program Satisfaction Questionnaire (PSQ), a 14-item measure that assesses both general program satisfaction (usefulness, acceptability) and perceived utility of program components (psychoeducation, EMA/EMI schedule).¹⁸ Measures selected were well-validated, have been administered to Veterans, and/or have been administered via telehealth.

Assessments completed via research staff:

Program Satisfaction Questionnaire (PSQ). Acceptability will be measured using an adaptation of the PSQ, a 14-item measure that assesses both general program satisfaction (usefulness, acceptability) and perceived utility of program components (psychoeducation, EMA/EMI schedule).¹⁸

Blessed Orientation-Memory-Concentration Test (BOMC). The BOMC will be used to screen for cognitive impairment (i.e., ≥ 11).¹⁹

Short Scale Anxiety Sensitivity Index (SSASI).²⁰ The SSASI is a 5-item self-report measure assessing fear of negative consequences of anxiety-related symptoms. Scores ≥ 9 on the SSASI are eligible.

The Anxiety Sensitivity Index-3 (ASI-3).²¹ The ASI-3 is an 18-item self-report measure assessing fear of negative consequences of anxiety-related symptoms.

The Intolerance of Uncertainty Scale-12 (IUS-12).²² The IUS-12 is a 12-item self-report measure assessing fear of uncertainty.

12-Item World Health Organization Disability Assessment Schedule (WHODAS) 2.0. The 12-item version of the WHODAS 2.0 assesses functional impairment across six domains: 1) understanding and communication, 2) self-care, 3) mobility, 4) interpersonal relationships, 5) work and household roles, and 6) community and civic roles.²³

PROMIS Profile-29²⁴. Used to assess the following domains: anxiety, depression, physical function, fatigue, sleep disturbance, ability to participate in social roles and activities, and pain interference.

Functional Impairment Due to COVID (FIDC).²⁵ A 7-item measure adapted from the WHODAS 2.0 to capture difficulties in functioning due to the COVID-19 pandemic, developed and validated by PI [name] and colleagues.

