COVID-19 Impact Battery (CIB) Worries.²⁵ An 11-item scale measuring distress and worry due to the COVID-19 pandemic.

COVID-19 Impact Battery (CIB) Behaviors.²⁵ A 12-item scale assessing avoidance behaviors in relation to the COVID-19 pandemic.

Depressive Symptom Index – Suicidality Subscale (DSI-SS). A 4-item measure assessing suicidality within the previous two weeks.

Demographics. At screening, we will assess participants' gender, age, educational background, employment, income, race, ethnicity, marital status, and socioeconomic status.

Exit Interview. The exit interview will assess overall impressions, impact of treatment, relationship with the therapist, and ways to improve the treatment. Acceptability will be measured using an 11-item adaptation of the Program Satisfaction Questionnaire (PSQ) that assesses both general program satisfaction (usefulness, acceptability) and perceived utility of program components (psychoeducation, EMA/EMI schedule).¹⁸ The exit interview and PSQ will inform further refinement of the intervention as needed with our stakeholders. The exit interview will also consist of a number of open ended questions, including prompts to ask for more information, to collect worthwhile feedback on the study procedures, intervention, and their overall feelings toward the intervention.

EMA Measures:

*State Short Scale Anxiety Sensitivity Inventory; SSAS*²⁰: measures anxiety sensitivity.

*State Penn State Worry Questionnaire; PSWQ*⁵¹: measures anxious apprehension.

State Anxiety Depression Distress Inventory-27; ADDI-27: measures anxious arousal

The PSWQ and ADDI-27 have been validated as measures of general anxious apprehension and anxious arousal, respectively, reflecting the two core anxiety dimensions underlying anxiety disorders.^{26,27} Participants will also rate their impairment across functional domains using the

12-item WHODAS 2.0. Visual analog scale (VAS) ratings from 1-100 will be used to assess anxiety, stress, and depression four times daily. ASI-3 items, revised to capture in-the-moment beliefs, will also be completed. Three items will be randomly selected from an ideographically developed pool of items the participant rates as impacting them “much” or “very much.” Thus, the pool of items to be drawn to potentially deliver EMI will differ by individual.

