All participants will be provided the VCL phone number at the end of each baseline assessment and at each follow-up assessment and encouraged to call the number should they become suicidal, simply wish to talk with someone, or would like assistance in obtaining a referral for mental health treatment. In situations in which potential suicide risk is identified during a phone call, we plan to use two levels of response: 1) researcher transfers the individual to the VCL (used in acute crises requiring emergency intervention or "rescue"); 2) researcher offers the participant a transfer to the VCL, but does not perform the transfer if he/she does not wish to be transferred (used in non-emergency situations).

Breach of Confidentiality. Statistical data files will be kept on VINCI project servers maintained by VINCI OI&T personnel and only summarized data without protected health information (PHI) will be downloaded from VINCI to local storage media. Research staff will use an audited VINCI download utility to move summarized data for reports, presentations and publications from VINCI servers to local storage media. The VINCI download utility provides an audit path including a copy of the downloaded material. The data extraction tool will be adapted for use with software directly available on the VINCI platform (e.g. Microsoft Word and Excel) and study data will be stored and maintained on VINCI. All study team personnel with access to sensitive patient data will stay current on their VA approved information security training and VA approved privacy policy training.

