Adverse Events (AE). All research staff will participate in an intensive training to help them understand the importance of reducing the risk for participants and learning how to recognize and report any AE or SAE. AEs may include, but are not limited to: worsened physical or mental health, or inadvertent disclosure of confidential research information. Serious Adverse Events (SAE) may include: death, hospitalization due to worsening psychiatric symptoms or suicidal ideation, or all life threatening or disabling/incapacitating events among research participants. Per IRB regulations, SAEs, any event resulting in a deviation from the study protocol (e.g., emergency hospitalization to address suicidal behaviors) or death will be reported to the PI within 24 hours and to the IRB in 48 hours. He will make a decision whether there is sufficient evidence to suspend data collection, allow for further IRB review, modify the protocol, or make other changes to reduce potential risk to participants. The study will resume based on agreement of the PI, and an IRB member (the chair will recuse himself because he is a co-I on the study). Immediate evaluation will occur to determine if any extra steps can be taken to minimize the likelihood of that type of AE occurring again. If changes can be made, a report/amendment will be written and submitted to the IRB. AEs that involve temporary distress will be noted by interviewers and provided to the IRB in an annual report.

Confidentiality of Records: Numerous protections are in place to reduce the likelihood of loss of confidentiality. All research data will be kept in locked filing cabinets in secure areas, absent of identifying information, and coded by research number only. Files containing consent forms and other items with identifying information will also be kept in locked filing cabinets, but these will be separate from cabinets containing data from this study. Social security numbers (SSNs) may be collected based on the participant's preferred payment methods. These SSNs would only be used as part of fiscal forms needed for payment, and these payment vouchers would be stored within protected electronic folders for documentation purposes only.

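### No question specific to adverse events, or tied to the exercises, covers the two weeks of daily home interoceptive exposure (IE)

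*Combined protocol and SAP*

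**What the plan says.** **Home exercises.** After the single telehealth session, section 5.1 (Face-to-face session) states: "Participants are also asked to complete one set of IE exercises daily for the next two weeks". In the session, IE consists of repeated hyperventilation plus a second chosen activity. The content of the home set is not itemised.

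**What the app records about them.** Section 5.1 (EMA): "event-based sampling will be used for tracking IE exercise completion". No item on how the exercise was tolerated is described.

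**Use of the incoming app data.** Section 4.0 has the coordinator trained "to monitor the data stream from the mobile app and contact participants as-needed when compliance issues for completion of surveys via mobile app arise". Survey compliance is the only stated reason for contacting a Veteran from that stream.

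**Next scheduled staff visit.** Section 5.1: "At the end of the two weeks, Veterans will complete a post-intervention assessment appointment". Visits at 1 and 3 months follow.

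**Exit interview, held at the post-intervention visit.** Section 5.5: "The exit interview will assess overall impressions, impact of treatment, relationship with the therapist, and ways to improve the treatment". It also has open questions with prompts. Its script is not in the text.

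**Adverse events.** Section 6.0 counts worsening of physical or mental health as an AE and has staff trained to recognise and report AEs. For temporary distress it says: "AEs that involve temporary distress will be noted by interviewers and provided to the IRB in an annual report". Under the Data Safety & Monitoring Plan, if no AE has occurred, the annual report to the IRB says so in a set sentence.

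**Why homework matters to the results.** Section 5.5: "Feasibility of BEAST will be indexed via participant retention, average homework completion, and percentage of EMA sessions completed".

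**The concern.** IE deliberately provokes bodily sensations, and most of it happens at home without a therapist. A pilot meant to refine the manual and app schedule for a larger trial should learn, in the same way from everyone, whether the home exercises caused unwanted reactions and whether any were abandoned because of them. The plan says who notes temporary distress but not what is asked, when, or on what form.

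Two outputs are affected. First, a statement that no AEs occurred is clear only if the reader knows each Veteran was asked about them. Second, a low homework-completion figure could mean forgetting, lack of time, technical trouble or unpleasant reactions. These call for different changes to the intervention. If the reasons are not asked for at the time, they cannot be recovered later.

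**Working it through.** The plan states no figure on this point, so there is none to reproduce. The check is a count of exposure and a comparison of each data source with what it would need to capture.

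**Exposure (section 5.1; sample size from sections 5.1 and 6.0)**
- Home IE sets per Veteran: 1 per day × 14 days = 14.
- Across the trial: 14 × 15 = 210.

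**App surveys over the same two weeks (section 5.1, EMA)**
- One morning survey plus three quasi-random surveys = 4 per day.
- Per Veteran: 4 × 14 = 56. Across the trial: 56 × 15 = 840.
- Check that these surveys run through the home period, using the compensation in section 5.6. Visits pay 40 + 40 + 30 + 30 = $140. A full EMA week pays 30 + 10 = $40. (340 − 140) / 40 = 5 weeks, which fits 1 baseline + 2 intervention + 1 + 1 follow-up weeks. The home IE weeks are covered.

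**Each source against the need**

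| Source | Asks every Veteran? | Tied to IE? | Named as AE source? | Physical reactions or stopped exercises? |
|---|---|---|---|---|
| IE entry in app (5.1) | Yes | Yes | No | No, completion only |
| EMA ratings: anxiety, stress, depression, arousal and others (5.5) | Yes | No | No | Not described |
| PROMIS-29 and DSI-SS, staff-read (5.5) | Yes | No | No | General domains and suicidality only |
| Exit interview (5.5) | Yes | Not in stated topics | No | May emerge from prompts; script not in the text |
| Interviewer noting (6.0) | Not stated | No | Yes | Not stated |

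No source combines a uniform question with a link to IE and a place in AE reporting. The clearest gap is physical reactions. They fall within the AE definition, but the expected risks listed under Protection Against Risk are psychological distress, frustration and fatigue, so nothing there prompts an interviewer to ask about them.

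The EMA ratings cannot fill the gap as described. The daytime surveys come 3 to 8 hours apart and are not said to be timed to IE. A raised rating does not by itself separate arousal that the exercise is meant to produce from an unwanted reaction. No AE review rule is given for these ratings.

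**The case against.** The strongest reply is that the plan already solicits a great deal. Through the home weeks each Veteran is due about 56 app surveys, with four daily ratings of anxiety, stress and depression, plus measures of arousal, worry, anxiety sensitivity and functioning. Staff read measures aloud at visits. The exit interview asks about the impact of treatment, with prompts, and raters bring its content to consensus.

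Other safeguards exist. The exercises are first practised with a therapist in a recorded session. Veterans are given the crisis-line number and "encouraged to call the number should they become suicidal, simply wish to talk with someone". The principal investigator tracks negative outcomes and meets staff regularly. Withdrawal for extreme distress is provided for. Suicidality procedures and serious-event reporting times are specified. The study is described as minimal risk and does not set out to estimate an AE rate. Even with complete capture, none in 15 would leave a one-sided 95% upper limit of 1 − 0.05^(1/15) = 18.1%.

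Most of this stands, and it rules out a stronger reading. A reader might infer that reactions come to light only if a Veteran volunteers them, mainly at about two weeks. The documents do not support that: the EMA ratings, the battery and the prompted interview are all solicited, and the EMA ratings run daily. A reader might also want to calculate how many reactions would be missed. The documents define no reaction and give neither a true rate nor a reporting share, so any such figure would be assumption throughout.

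What the reply does not supply is a question about the home exercises themselves. The unseen interview script or emergency procedures might contain one; the protocol body does not describe it.

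**Conclusion.** The narrow point holds. For two weeks of daily home IE, the protocol body describes no AE-specific or IE-linked question. Physical reactions and exercises stopped early have no described structured capture.

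Its size is modest: 14 requested sets per Veteran, 210 in all, in a 15-person single-arm pilot. The effect is on how far a no-AE statement and the homework index can be interpreted. It does not touch any analysis result, the serious-event procedures or the suicidality procedures. It is a gap in systematic capture and does not show that Veterans are harmed or go unmonitored.

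The conclusion rests on two assumptions: that the exit-interview script contains no such item, and that homework completion, which the plan does not define further, includes the IE sets. If the script already asks the question uniformly, all that remains is to say so in the protocol and link the answers to AE reporting. This is an improvement worth considering rather than a required correction.

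**What to change.** At the post-intervention visit, ask every Veteran one short structured question covering two things: any unwanted physical or emotional reaction to the home IE exercises, and any exercise stopped early, with the reason. Repeat it at 1 and 3 months only for Veterans still doing IE, since the plan requests IE for two weeks only.

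Report the answers separately from spontaneously reported AEs, so that solicited and unsolicited counts are not mixed. Use them when interpreting homework completion, and review them at the existing meetings of the principal investigator and staff (Data Safety & Monitoring Plan).

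**Cost.** A line of protocol wording and one item at visits where staff already read measures aloud. The post-intervention visit gives 15 askings. The ceiling is 15 × 3 = 45, reached only if every Veteran continues IE to both follow-ups. At an assumed minute each, that is 15 to 45 minutes of interview time for the whole trial. The other cost is a less favourable AE count, because asking tends to bring out more than noting does. The question improves completeness, not timing: it does not bring reactions to light sooner.
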